7.3.3 Investigator Assessment

7.3.3.1 Investigators Global Assessment (IGA)

This is not an efficacy study, and therefore the Investigators Global Assessment is done for informational purposes. The evaluations should be performed by the Principal Investigator or appropriately qualified Sub-Investigator at each visit. **It is important that the same evaluator performs the evaluations for the same subject at each visit, however it may not be feasible in all instances. Every effort should be made to maintain consistency of the evaluator for each subject.**

CONFIDENTIAL

Version Date: 07 March 2017

The IGA is intended for the global evaluation of papulopustular rosacea. Background non-transient erythema and telangiectasias should not be assessed as part of the IGA. The IGA score represents the subject's condition at the time of the evaluation.

The following categories will be used from the IGA scale to perform the global evaluation of papulopustular rosacea:

Investigators Global Assessment (IGA) Scale

Grade	Grading Scale Score	Description of Papulopustular Rosacea Disease Status
Clear	0	No inflammatory papules or pustules.
Almost clear	1	Very few with 1 or 2 inflammatory papules/pustules.
Mild	2	Several (3-10) small inflammatory papules/pustules.
Moderate	3	11 to 19 small or large inflammatory papules/pustules and no nodules.
Severe	4	Numerous (≥ 20) small and or large inflammatory papules/pustules, and up to 2 nodules, (at baseline).

7.4 SAFETY VARIABLES

7.4.1 Medical / Medication History and Demographics

A medical history including rosacea history, a medication history (including known rosacea treatments used in the last 5 years) will be performed, as well as collection of demographic information at the Screening visit. Medical and medication history will be updated at the Baseline visit. Demographic information will include the subject's age, sex, race, ethnicity and Fitzpatrick skin type (Appendix B). Skin type will be collected based on the subject reported skin type.

7.4.2 Limited Physical Exam

A limited physical exam, will be performed at the Screening Visit (including height and weight) and at the final Month 12 Visit (End of Treatment Visit or Early Termination Visit), including weight will be performed. The limited Physical Exam should include an assessment of the following:

- General Appearance
- Head
- Eyes

CONFIDENTIAL

Version Date: 07 March 2017

- Ears
- Nose
- Throat
- Lungs
- Heart
- Skin

7.4.3 Vital Signs

Vital signs (blood pressure, respirations, heart rate) will be measured at the Screening Visit, Month 6 and Month 12 (Final or Early Termination) Visit.

7.4.4 Clinical Laboratory Testing

Blood samples (approximately 11 mL) will be collected at Screening and the Month 12 Visit (Early Termination, or Final/EOT Visit), for hematology and chemistry laboratory analysis (total expected volume of approximately 22 mL). A central laboratory will perform the sample analysis for all study sites. Instructions for sample collection, preparation, labeling, and shipping will be provided by the laboratory.

All laboratory values that are considered clinically significant will be reported as an adverse event and followed as such. The following parameters will be determined:

- Hematology: Complete blood count (CBC), including hemoglobin, hematocrit, red blood cell (RBC), white blood cell (WBC), count with differential, and platelet count.
- Blood Chemistry/Lipids: sodium, potassium chloride, bicarbonate or carbon dioxide, glucose, blood urea nitrogen (BUN), creatinine, calcium, uric acid, total bilirubin, total protein, albumin, aspartate aminotransferase (AST), alanine aminotransferase (ALT), alkaline phosphatase, gamma glutamyl transferase (GGT), total cholesterol, high-density lipoproteins (HDL), low-density lipoproteins (LDL), triglycerides, and lactic dehydrogenase (LDH).

7.4.5 Immunogenicity Testing

Blood samples (approximately 6 mL) will be collected at Day 1 (Pre-dose), Month 1, 3, 6, 9 and 12 for immunogenicity testing (total expected volume of approximately 40 mL). Samples from all sites will be shipped to a central laboratory and stored for sample analysis. Instructions for sample collection, preparation, labeling, and shipping will be provided by the laboratory. Sample testing will occur periodically dependent upon assay development and when an adequate number of samples have been received at the laboratory. The assay configuration provides for a screening and confirmatory assay. Any positive anti-drug antibody assay results from confirmatory testing will be made available once known. It is intended to follow any subjects with positive confirmatory anti-drug antibody assay results for up to 1 year from discovery to allow for reactive

CONFIDENTIAL

Version Date: 07 March 2017

antibody results to return to baseline. Any subjects with positive confirmatory anti-drug antibody assay results who have completed the study or discontinued from the study for any reason, will be contacted and requested to return to the clinical study site for additional immunogenicity testing as noted previously.

7.4.6 Urine Pregnancy Test

An in-office, highly sensitive urine pregnancy test must be performed for all female subjects of child-bearing potential at Screening and the Month 12 Visit (Early Termination, or Final Visit). All female subjects of child bearing potential must have a negative urine pregnancy test prior to receiving study drug. Urine pregnancy testing should also be conducted for any female who is suspected of being pregnant. Any female who becomes pregnant should be withdrawn from the study and followed to term. The CRO/Sponsor must be notified of any pregnancy that occurs while on therapy. In the event of pregnancy, the site will complete a pregnancy report form to capture the pregnancy outcome.

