7.2 SELECTION OF STUDY POPULATION

7.2.1 Inclusion Criteria

Subjects must meet each of the following criteria to be considered eligible for entry into the study:

1. Subjects who have provided written informed consent to participate in the study.
2. Healthy, male and nonpregnant female subjects, 18 years of age or older.
3. A diagnosis of severe papulopustular rosacea using the Investigator Global Assessment (IGA) grading scale (Grade 4; described as numerous (≥ 20) small and or large inflammatory papules/ pustules, and up to 2 nodules, (at baseline))
4. Subjects with the presence of telangiectasia at Baseline
5. Subjects with the presence of facial erythema associated with their rosacea at Baseline
6. Non-nursing, female subjects of child bearing potential, who are using a highly effective form of birth control or females not of childbearing potential due to menopause (must be postmenopausal for at least one year).
 - Highly effective methods of birth control are defined as those, alone or in combination, that result in a low failure rate (i.e. less than 1% per year) when used consistently and correctly. Forms of birth control include: Oral (birth control pills), Intravaginal: (e.g. NuvaRing®), Implantable (e.g. Norplant®), injectable (e.g. Depo-Provera®) or transdermal (e.g. Ortho Evra®) contraception; intrauterine device (IUD); double-barrier (diaphragm or condom with spermicidal gel or foam); for two months prior to study enrollment or a vasectomized partner or true abstinence (in line with preferred and usual lifestyle of subject) with an acceptable form of birth control should

CONFIDENTIAL

Version Date: 07 March 2017

the subject become sexually active. Periodic abstinence (e.g., calendar, ovulation, symptothermal, post-ovulation methods) and withdrawal are not acceptable methods of contraception. All female subjects of child bearing potential must undergo an in-office, highly sensitive urine pregnancy test, with a negative result, prior to receiving study drug. In addition, women of childbearing potential must agree to have a highly sensitive urine pregnancy test at the end of the study.

7. Subjects who are willing and able to return to the study clinic for the designated study visits.
8. Subjects who are willing to refrain from sunbathing, using sun tanning booths/beds, or excessive exposure to the sun for the duration of the study.
9. Subjects who are willing to comply with the protocol and visit requirements.

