7.2.2 Exclusion Criteria

Subjects are not eligible to participate in the study if any of the following are present:

1. Subjects with clinically significant abnormal findings at the Screening or Baseline/Day 1 Visit that would require a new intervention or treatment or a change in treatment that would in the opinion of the investigator supersede participation in the clinical trial.
2. Subjects with steroid rosacea or subtype 3 (phymatous rosacea).
3. Subjects with nodular rosacea (defined as more than 2 lesions greater than 5 mm).
4. Subjects with underlying diseases or other dermatological conditions, such as; atopic dermatitis, perioral dermatitis, or seborrheic dermatitis, which requires the use of interfering topical or systemic therapy or may interfere with the rosacea diagnosis or its assessment.
5. Subjects with known allergies to the active ingredient or any of the excipients. (See Section 7.5.2)
6. Subjects who have not undergone the specified washout period(s) for the following topical preparations applied to the face or subjects who require the concomitant use of any of the following topical preparations/treatments applied to the face:

Product Washout Period
(Prior to Baseline/First Dose)

- Abradants, astringents, toners, facials, masks, or moisturizers containing retinols, AHA (alpha hydroxyl acids), salicylic acids
 - Tanning booths/beds 1 week
 - Antibiotics (other than topical ocular application) 2 weeks
 - Antimicrobial soaps 2 weeks
 - Corticosteroids 2 weeks
 - Other anti-inflammatories 2 weeks
 - Other rosacea treatments (e.g., azelaic acid, metronidazole, ivermectin, sulfacetamide) 2 weeks
 - Retinoids 4 weeks
7. Subjects who have not undergone the specified washout period(s) for the following systemic treatments or subjects who require the concomitant use of any of the following systemic treatments:

Product Washout Period
(Prior to Baseline/First Dose)

- Antibiotics 4 weeks
 - Corticosteroids 4 weeks
 - Retinoids 4 weeks
8. Female subjects who are pregnant, nursing, or planning a pregnancy within the study period.
9. Subjects using an investigational drug within 30 days of the Baseline Visit or who are currently participating in an investigational study. Use of an investigational drug/device and/or participation in another investigational study is prohibited during this study.
10. Subjects who currently abuse alcohol or drugs or who have a history of chronic alcohol or drug abuse with in the past year.

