7.3 CONDUCT OF STUDY

7.3.1 Table of Study Procedures

Procedures	Screening (Within 30 days of Baseline)	Baseline (Day 1)	Interim Visits: Month 1, 3, 6, and 9 (Week 4, 12, 26 and 39 ± 14 days) or Unscheduled Visit	Final Visit: Month 12/EOT (Week 52 ± 14 days)
Informed Consent	X			
Demographics, Medical and Rosacea History	X	X		
Limited Physical Exam including weight	X (including height)			X
Vital signs	X		X (Month 6 only)	X
Blood collection for Clinical Laboratory Test (hematology, chemistry)	X			X
Blood collection for immunogenicity testing		X	X	X
Urine Pregnancy Test, if applicable	X			X
Investigator Global Assessment	X	X	X	X
Inclusion/Exclusion Criteria	X	X		
Weigh Tubes/Dispense Study Drug		X	X	
Dispense Diaries		X	X	
Collect Diaries			X	X
Instruct on Treatment Application		X	X	
Apply Study Drug		X	X	X
Collect drug/ Drug Accountability/ Compliance check			X	X
Previous/Concomitant Medication/Therapy Review	X	X	X	X
Adverse Event Assessment		X ¹	X	X

¹ Adverse event assessment during the Baseline visit will be performed following the first application of study drug.

CONFIDENTIAL

Version Date: 07 March 2017

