7.3.2.1 Screening Visit

The following procedures will be performed during the Screening visit:

- Obtain subject's written informed consent prior to initiating any study procedures, including instructing the subject to discontinue use of medication that requires a washout (see Section 7.5.9.1). Provide subject with a copy of signed and dated consent form. Document subject's informed consent in the subject's medical record.
- Screen the potential subject according to the study inclusion/exclusion criteria.
- Schedule the Baseline/Day 1 visit to occur after the results of the laboratory safety testing are received and any required washout period is completed.
- Record Demographic information including age, sex, race, ethnicity and Fitzpatrick skin type (Appendix B)
- Record medical history. Include information on: subject's history of rosacea and any previous therapies, including:
 - The approximate date of physician's diagnosis of rosacea;
 - The subject reported signs and symptoms of rosacea,
 - How often they experience these symptoms?
 - Whether symptoms are continuous or occasional?
 - What, if anything, appears to trigger or worsen these symptoms?
 - sunlight
 - stress
 - alcohol
 - exercise
 - hot and cold temperatures
 - spicy food
 - Rosacea therapies within the previous 5 years.
- Review and record concomitant medications/therapies used in the last 30 days.
- Assess whether the subject will require a washout period
- Perform a limited Physical Exam (refer to Section 7.4.2) with vital signs, height and weight measurements.
- Obtain a blood sample for hematology and chemistry analysis.
- Perform an in-office urine pregnancy test on all females of childbearing potential.
- Perform the Investigators Global Assessment (IGA) of rosacea. **It is important that the same evaluator performs the evaluations for the same subject at each**

CONFIDENTIAL

Version Date: 07 March 2017

visit, however it may not be feasible in all instances. Every effort should be made to maintain consistency of the evaluator for each subject.

- Schedule the next visit.

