7.3.2.2 Baseline Visit (within 30 days of Screening)

- Review the study inclusion/exclusion criteria to confirm eligibility, including review of the laboratory results for any clinically significant findings that would exclude the subject from eligibility for the study.
- Review and record any changes since the first visit in medications/therapies, and the subject's health.
- Obtain a blood sample for immunogenicity testing
- Perform the Investigators Global Assessment (IGA) of rosacea. **Every effort should be made to maintain consistency of the evaluator for each subject.**
- If the subject has fulfilled the eligibility requirements, as stated in the inclusion/exclusion criteria, provide the subject four tubes of omiganan topical gel. Record the subject number and dispensing date on the tubes that are assigned to that subject. Record the dispense date and the subject number on the source document.
- First Treatment Application –
 - Weigh the tubes that are designated to be dispensed to the subject prior to the subject applying their first dose of study medication. The tubes should be weighed with the cap on as outlines in section 7.5.7.
 - Give the subject a copy of the treatment application instructions (see Appendix A) and allow the subject take time to read them. Provide instruction to the subject on the daily application of study drug and confirm the subjects understanding of the instructions.
 - Record the Subject # and date of dispensing on the tube labels and dispense the tubes to the subject.
 - The subject should be instructed to apply the treatment once daily, preferably each morning, at approximately the same time for the duration of the study. A thin layer of the assigned study drug (approximately 0.4 gm) should be applied to the subject's face, including the non-affected areas (as described in Appendix A). The subject should be reminded to use all of the contents of one tube before they start using a new tube from their dispensed supply
 - Under the supervision of the study coordinator or designee, the subject should apply the first dose of study drug at the study site and the observer should observe that the subject applies a thin layer to the entire face as per the treatment application instructions (see Appendix A).
- Instruct the subject on the use of the daily diary and dispense the diary.

CONFIDENTIAL

Version Date: 07 March 2017

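### No pregnancy test is scheduled at Baseline: the Screening result that clears a woman for her first dose may be 30 days old

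*Protocol*

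**What the plan says.** **Criterion.** Exclusion 8 in Protocol 7.2.2 rules out "Female subjects who are pregnant, nursing, or planning a pregnancy within the study period".

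**Confirmation at Baseline.** The first step of the Baseline visit in 7.3.2.2 is: "Review the study inclusion/exclusion criteria to confirm eligibility, including review of the laboratory results for any clinically significant findings". The 7.3.1 table also marks inclusion/exclusion criteria at both Screening and Baseline. The Baseline list includes an update on the subject's health and medications, but no pregnancy test.

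**Test schedule.** Section 7.4.6 states: "An in-office, highly sensitive urine pregnancy test must be performed for all female subjects of child-bearing potential at Screening and the Month 12 Visit", and extends the later test to early termination. The row "Urine Pregnancy Test, if applicable" in 7.3.1 carries two marks. The visit lists place them at Screening (7.3.2.1) and the final visit (7.3.2.4). The interim list (7.3.2.3) has none.

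**Negative result before dosing.** Inclusion 6 in 7.2.1 asks for a "highly sensitive urine pregnancy test, with a negative result, prior to receiving study drug". Section 7.4.6 repeats the requirement. Neither gives a maximum age for the result.

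**Interval.** Both 7.3.1 and the heading of 7.3.2.2 allow 30 days between Screening and Baseline.

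**Other safeguards.** Section 7.4.6 calls for a test in any woman suspected of being pregnant. Inclusion 6 requires highly effective contraception, defined by a failure rate below 1% per year with consistent and correct use.

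**The concern.** Pregnancy status can change between Screening and Day 1, and it is confirmed on Day 1 without the objective test that the protocol relies on elsewhere. Reviewing laboratory results and asking about health will not reveal an early pregnancy that the woman herself does not suspect.

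The long interval is partly built in. Consent must come before any instruction to stop a drug that needs washout, and Baseline must wait until washout is complete (7.3.2.1). Facial retinoids and systemic antibiotics, corticosteroids and retinoids each need 4 weeks (7.2.2). A woman still using one of these at Screening therefore has her first dose about 28 to 30 days after her only test.

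Each case would be an ineligible subject enrolled and exposed to study drug, then withdrawn and followed to term under 7.4.6, with no documented negative test at the time of first exposure. After Day 1 the next scheduled test is at Month 12 or early termination. In between, a missed pregnancy comes to light only on suspicion.

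**Working it through.** **Step 1: can a pregnant woman be dosed with the plan followed exactly?** Take each possible state on Day 1 in turn.

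- Pregnant and detectable at Screening: caught by the Screening test.
- Pregnancy known by Day 1: caught by exclusion 8 at the Baseline review.
- Pregnancy suspected by Day 1: caught by the for-cause test in 7.4.6.
- Conceived after Screening, or too early to detect then, and neither known nor suspected: the Screening negative satisfies inclusion 6 and 7.4.6, the Baseline review has nothing to act on, and she is dosed.

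Only the last state passes through.

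**Step 2: how many such cases?** The plan gives no figure to reproduce, so this is for scale only.

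Inputs:

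- Annual rate r: 1%, the protocol's ceiling (7.2.1).
- Interval: 30 days, the maximum (7.3.1, 7.3.2.2).
- Number of women of childbearing potential, N: not stated. I assume 100 to 200 of the planned maximum of 300 subjects.

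Expected conceptions in the interval = N × r × 30/365.

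- N = 100: 100 × 0.01 × 30/365 = 0.08
- N = 200: 200 × 0.01 × 30/365 = 0.16

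Chance of at least one = 1 − (1 − r)^(N × 30/365.25).

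- N = 100: 1 − 0.99^8.21 = 7.9%
- N = 200: 1 − 0.99^16.43 = 15.2%

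**Step 3: sensitivity to the assumptions.**

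| Assumed annual rate | Days between test and first dose | Expected, N = 100 | Expected, N = 200 |
|---|---|---|---|
| 0.5% | 30 | 0.04 | 0.08 |
| 1% (protocol ceiling) | 14 | 0.04 | 0.08 |
| 1% (protocol ceiling) | 30 | 0.08 | 0.16 |
| 5% | 30 | 0.41 | 0.82 |

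The 0.5% and 5% rates and the 14-day wait are my assumptions. The protocol's 1% applies to consistent and correct use, so a higher rate is possible in practice, but the documents supply none. Every 30-day row assumes that all women wait the full window, which overstates the count. No row includes pregnancies already present but undetectable at Screening, which understates it.

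**The case against.** The strongest reply is that the protocol is consistent with itself. The table, the visit lists and 7.4.6 place the test at the same two visits, and a Screening negative does precede study drug. That stands: a reader might infer a contradiction between the Baseline confirmation and the test schedule, and the text does not show one.

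A reader might also infer that any woman pregnant on Day 1 would get through. The documents do not support that. The Screening test, exclusion 8 and the for-cause test catch the detectable, known and suspected cases, and the contraception criterion makes the remainder uncommon.

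Nor do the documents support saying that the timing of conception relative to first dose could never be determined. Section 7.4.6 requires follow-up to term and a pregnancy report, which may help with dating. What is missing is a documented test at first exposure, and even a negative Baseline test would not settle the timing of a very recent conception.

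Further points stand and limit the size. Most listed topical washouts are 1 or 2 weeks. The 4-week washouts count back from Baseline, so a woman who stopped the drug before Screening can have a shorter wait. Section 5.1 reports no detected systemic absorption, including in a maximum-use study. The analysis is descriptive (7.6.1), so no planned inference depends on this. None of these points closes the gap in the last state of Step 1.

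**Conclusion.** The point holds in a narrow form. The only scheduled pre-dose pregnancy test may be 30 days old when the first dose is applied, so an unsuspected early pregnancy can satisfy every written requirement even though exclusion 8 is confirmed again at Baseline.

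The expected number is small: 0.08 to 0.16 cases in the study. That rests on the protocol's 1% ceiling, an assumed 100 to 200 women of childbearing potential, and a full 30-day wait for all of them, and it omits pregnancies too early to detect at Screening. The case for changing the plan is subject safety at very low cost. It does not rest on any effect on the study's analyses.

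**What to change.** The sponsor should reconcile the test timing (inclusion 6, 7.3.1, 7.4.6) with the Baseline confirmation of eligibility (exclusion 8, 7.3.1, 7.3.2.2). Keep the Screening test and add the same in-office urine test in three places: the Baseline column of 7.3.1, the eligibility step of 7.3.2.2, and 7.4.6. The protocol's existing requirement for a negative result before study drug would then be met by a current one. The Screening test should stay, because it finds a pregnancy before the woman goes through washout and blood sampling.

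The cost is one table cell, matching text in two sections, and one urine stick per woman of childbearing potential at a visit she already attends. There are two limits. A Baseline test still cannot detect the most recent conceptions, and it does nothing about the interval from Day 1 to the next scheduled test at Month 12 or early termination.
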